## 6.3 Influenza Immunogenicity Population

The Influenza Immunogenicity Population is a subset of the mITT Population that includes only subjects who received both vaccines, provide visit 1 and visit 2 blood draws available with HAI titer results for analysis within the protocol-defined time frame, did not have an influenza or SARS-CoV-2 infection between visits 1 and 2, and had no protocol violations affecting immunogenicity. Protocol violations affecting the immunogenicity analyses are defined in the Statistical Analysis Plan (SAP) Appendix 1. The acceptable visit window for sample analysis will be +14 days from the target date. Should 10% or more of the total study population be excluded from the Influenza Immunogenicity Population due to missing the visit window, then an additional analysis will be performed including these subjects with the missing visit window exclusion.

## 6.4 SARS-CoV-2 Immunogenicity Population

The SARS-CoV-2 Immunogenicity Population is a subset of the mITT Population that includes only subjects who received both vaccines, provide visit 1 and visit 2 blood draws available with MSD results for analysis within the protocol-defined time frame, did not have an influenza or SARS-CoV-2 infection between visits 1 and 2, and had no protocol violations affecting immunogenicity. Protocol violations affecting the immunogenicity analyses are defined in the Statistical Analysis Plan (SAP) Appendix 1. The acceptable visit window for sample analysis will be +14 days from the target date. Should 10% or more of the total study population be excluded from the SARS-CoV-2 Immunogenicity Population due to missing the visit window, then an additional analysis will be performed including these subjects with the missing visit window exclusion.

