Group i: Concomitant administration of mRNA COVID-19 vaccine and quadrivalent influenza vaccine

- Take temperature and review temporary delay criteria
- Collect whole blood for sera sample (**Section 5.5.4.1**) and PBMC and plasma samples (in subset of participants, target n=250; 200 adults and 50 children) (**Section 5.5.4.2**)
- Confirm date of next appointment on day 56 of study

Group ii: Sequential administration of quadrivalent influenza vaccine then mRNA COVID-19 vaccine

- Take temperature and review temporary delay criteria
- Collect whole blood for sera sample (**Section 5.5.4.1**) and PBMC and plasma samples (in subset of participants, target n=250; 200 adults and 50 children) (**Section 5.5.4.2**)
- Administer mRNA COVID-19 vaccine
- Confirm date of next appointment on day 56 of study

Group iii: Sequential administration of mRNA COVID-19 vaccine then quadrivalent influenza vaccine

- Take temperature and review temporary delay criteria
- Collect whole blood for sera sample (**Section 5.5.4.1**) and PBMC and plasma samples (in subset of participants, target n=250; 200 adults and 50 children) (**Section 5.5.4.2**)
- Administer quadrivalent influenza vaccine (Flucelvax [cclIV4])
- Confirm date of next appointment on day 56 of study

Visit 3; study day 56 (56-120) – Specimen Collection – Clinic Visit

- Collect whole blood for sera sample (**Section 5.5.4.1**) and PBMC and plasma samples (in subset of participants, target n=250; 200 adults and 50 children) (**Section 5.5.4.2**)
- Confirm date of next appointment on day 180 of study

Visit 4; study day 180 – Specimen Collection – Clinic Visit

- Collect whole blood for sera sample (**Section 5.5.4.1**) and PBMC and plasma samples (in subset of participants, target n=250; 200 adults and 50 children) (**Section 5.5.4.2**)

Table 2: Schedule of Qualifying ARI Events		
Procedure	Acute Visit	Convalescent Visit
	Clinic	Clinic
Estimated Study Day	< 10 days after symptom onset	28 days after Acute Visit
Time Following Acute Visit (Days) [Window]	0	28 [28-42]
Nasal swab collection for viral testing	X	
Whole blood collection for sera sample	X	X

Table 2: Schedule of Qualifying ARI Events		
Procedure	Acute Visit	Convalescent Visit
	Clinic	Clinic
Estimated Study Day	< 10 days after symptom onset	28 days after Acute Visit
Time Following Acute Visit (Days) [Window]	0	28 [28-42]
Whole blood collection for PBMC and plasma sample	X	X

Acute Visit; <10 Days after Symptom Onset – Specimen Collection – Clinic Visit

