## 1 INTRODUCTION

This document describes the statistical procedures that will be utilized for the study of Comparative Immunogenicity of Concomitant vs Sequential mRNA COVID-19 and Influenza Vaccinations. This statistical analysis plan (SAP) describes the methods of statistical analysis. In this study, participants will be randomly assigned to receive an approved quadrivalent cell culture-based influenza vaccine (cclIV4) and mRNA COVID-19 vaccine (Moderna) either concomitantly or sequentially, 28 days apart. Participants (aged 6-11 years and 18-64 years) will be enrolled in the 2023-2024 influenza season. Enrolled participants will be randomized to one of the following interventions (2:1:1) using a permuted block method stratified by age group (aged 6-11 years and 18-64 years) and site: (1) concomitant administration of the mRNA COVID-19 vaccine (Moderna) and quadrivalent influenza vaccine (cclIV4); (2) sequential administration of the quadrivalent influenza vaccine (cclIV4) at Visit 1 (day 0) and the mRNA COVID-19 vaccine (Moderna) at Visit 2 (day 28); (3) sequential administration of the mRNA COVID-19 vaccine (Moderna) at Visit 1 (day 0) followed by the quadrivalent influenza vaccine (cclIV4) at Visit 2 (day 28).

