## 9 ANALYSIS OF STUDY OBJECTIVES

### 9.1 Primary Objective

The primary objective will be analyzed using the immunogenicity population. All endpoints will be assessed with two-sided tests and alpha set to 0.05.

*Endpoint i:*

The proportion of participants with a seroprotective HAI before and 28-42 days after immunization will be compared between group i (concomitant administration) and ii (influenza administered first), using the following null ( $H_0$ ) and alternative ( $H_1$ ) hypotheses:

$H_0$ : Simultaneous group – Sequential group = 0

$$H_0: \pi_1 - \pi_2 = 0$$

$$H_1: \pi_1 - \pi_2 \neq 0$$

where  $\pi$  is the seroprotective rate.

P values and confidence intervals for the geometric mean titer ratio will be estimated using a logistic regression adjusted for site.

*Endpoint ii:*

The proportion of participants achieving seroconversion will be compared between group i (concomitant administration) and ii (influenza administered first), using the following null ( $H_0$ ) and alternative ( $H_1$ ) hypotheses:

$H_0$ : Simultaneous group – Sequential group = 0

$$H_0: \pi_1 - \pi_2 = 0$$

$$H_1: \pi_1 - \pi_2 \neq 0$$

where  $\pi$  is the seroconversion rate.

P values and confidence intervals for the geometric mean titer ratio will be estimated using a logistic regression adjusted for site.

*Endpoint iii:*

GMTs before and 28-42 days after immunization will be compared between group i (concomitant administration) and ii (influenza administered first), using the following null ( $H_0$ ) and alternative ( $H_1$ ) hypotheses:

$$H_0: \mu_1 / \mu_2 = 1$$

$$H_1: \mu_1 / \mu_2 \neq 1$$

where  $\mu$  is the geometric mean titer.

P values and confidence intervals for the geometric mean titer ratio will be estimated using a generalized estimating equation linear regression accounting for site clustering.

*Endpoint iv:*

Geometric mean fold rise will be compared between group i (concomitant administration) and ii (influenza administered first), using the following null ( $H_0$ ) and alternative ( $H_1$ ) hypotheses:

$$H_0: \mu_1 / \mu_2 = 1$$

$$H_1: \mu_1 / \mu_2 \neq 1$$

where  $\mu$  is the geometric mean fold rise.

P values and confidence intervals for the geometric mean titer ratio will be estimated using a linear regression adjusted for site.

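### The infection exclusion in SAP 6.3 and 6.4 covers Visits 1-2 in every arm, so it misses the response interval (Visits 2-3) of the later-dosed arm in the exploratory analyses; the primary HAI contrast is not affected

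*SAP*

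**What the plan says.** The influenza population (SAP 6.3) and the SARS-CoV-2 population (SAP 6.4) are defined in the same way for all three arms.

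- **Infection.** Both sections admit only participants who "did not have an influenza or SARS-CoV-2 infection between visits 1 and 2".
- **Samples.** SAP 6.3 requires that participants "provide visit 1 and visit 2 blood draws available with HAI titer results for analysis within the protocol-defined time frame". SAP 6.4 requires that they "provide visit 1 and visit 2 blood draws available with MSD results for analysis within the protocol-defined time frame". Neither names Visit 3.
- **Dosing.** In SAP 1, group ii receives "the mRNA COVID-19 vaccine (Moderna) at Visit 2 (day 28"), and in group iii COVID-19 vaccine is "followed by the quadrivalent influenza vaccine (cclIV4) at Visit 2 (day 28"). Protocol 5.4.1 agrees; its Visit 2 procedures include the heading "Group ii: Sequential administration of quadrivalent influenza vaccine then mRNA COVID-19 vaccine".
- **Primary analysis.** In SAP 9.1 each of the four HAI endpoints "will be compared between group i (concomitant administration) and ii (influenza administered first").
- **Exploratory serology.** SAP 9.2 uses the immunogenicity population. It carries the primary methods over to MN, SARS-CoV-2 and circulating-virus objectives without restating the arms. In SAP 3.2, EO3 and EO4 report titres by vaccination group at every visit including Visit 3, and EO5 and EO6 use Visits 1 to 3.
- **Appendix 1.** The listed violations include missed visits, out-of-window visits, and a missing pre- or post-vaccination draw for the respective vaccine. Infection is not on the list.

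**The concern.** The exclusion presumably exists so that the post-dose titre reflects the vaccine and not an infection between dose and sample. A rule fixed to Visits 1-2 does that only for a vaccine given at Visit 1.

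Take COVID-19 vaccine. A group i participant infected with SARS-CoV-2 between dose and first post-dose sample is removed. A group ii participant with the same event, between Visits 2 and 3, stays in. The same holds for influenza vaccine in group iii compared with groups i and ii.

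Selection then depends on arm. If infection raises titre, it can raise the later-dosed arm only, and concomitant dosing looks worse by comparison. Randomisation gives no protection, because the selection is applied after it.

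**Working it through.** The plan states no figure on this point, so there is nothing to reproduce. The check is to set the rule against each arm's response interval, find which analyses are exposed, and gauge the size.

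**1. Does the rule fit the interval?**

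| Vaccine studied | Arm | Dose | First post-dose sample | Infection excluded in that interval? |
|---|---|---|---|---|
| Influenza | i, ii | Visit 1 | Visit 2 | Yes |
| Influenza | iii | Visit 2 | Visit 3 | No |
| COVID-19 | i, iii | Visit 1 | Visit 2 | Yes |
| COVID-19 | ii | Visit 2 | Visit 3 | No |

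**2. Which analyses use the two exposed rows?**

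- Primary HAI endpoints: group i v ii only, so neither exposed row is used.
- Group iii after influenza vaccine: the by-group results in EO3 and EO5. The SAP names no contrast that uses this response. Protocol 5.2.1.1 and 8.2 speak generally of comparing concomitant with sequential groups.
- Group ii after COVID-19 vaccine: EO4 by group, and EO6. Its only early post-dose sample is Visit 3. The SARS-CoV-2 contrast uses it if SAP 9.2 carries over i v ii literally, but not if i v iii is meant. Protocol 5.2.2.2 does not say which sequential arm.

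The asymmetry appears when arms are compared at their first post-dose sample. At Visit 3 itself, no arm has Visit 2-3 infections removed.

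**3. How large could it be?**

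Assumed, because the documents give neither:
- *p*, the share of the later-dosed arm infected with the virus in question between Visits 2 and 3: 2-10%
- *k*, the mean fold increase in titre from infection: 2 to 4

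All such infections are taken as removed in the comparison arm. On the log scale the mean rises by p × log(k), so the GMT inflation factor is k^p.

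| p | k = 2 | k = 4 |
|---|---|---|
| 0.02 | 1.014 | 1.028 |
| 0.05 | 1.035 | 1.072 |
| 0.10 | 1.072 | 1.149 |

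The inflation is 1.4% to 15%. The ratio of group i to the later-dosed arm would be multiplied by 1/1.014 = 0.986 at the low end and 1/1.149 = 0.870 at the high end.

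Groups ii and iii are each planned at 150 adults + 50 children = 200, so 2-10% is 200 × 0.02 = 4 to 200 × 0.10 = 20 people. Assays run on a subset would include fewer.

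**4. How long is the interval?**

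Protocol 5.4.1 sets Visit 3 at "study day 56 (56-120"), and its Table 1 allows 28 to 92 days after Visit 2. SAP 6.3 and 6.4 allow +14 days from target, which is 28 + 14 = 42 days if applied to Visit 3. If the risk is 3% per 28 days (also assumed):
- 42 days: 1 − 0.97^(42/28) = 4.5%
- 92 days: 1 − 0.97^(92/28) = 9.5%

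With Appendix 1 removing out-of-window visits, the shorter interval is the more likely one for analysis.

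**The case against.** **The primary analysis is sound.** A reader might infer that the trial's main comparison is biased. It is not: groups i and ii both receive influenza vaccine at Visit 1, so the Visit 1-2 rule is right there. This stands in full.

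**The SARS-CoV-2 contrast may be i v iii.** The primary design compares concomitant dosing with the arm given the studied vaccine first. By analogy the COVID-19 contrast is i v iii, and the Visit 1-2 MSD requirement in SAP 6.4 suits that. On this reading the contrast has no asymmetry. But the SAP does not say so, and group ii's EO4 results would still be reported from a population screened only to Visit 2. This stands in part.

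**Missing Visit 3 samples.** A reader might infer that people without a Visit 3 sample distort the later-dosed result. Appendix 1 already removes missed visits and missing draws for the respective vaccine. SAP 7.2 imputes nothing, so such a person adds no post-dose titre. What remains is unclear wording in 6.3 and 6.4.

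**Infections are monitored.** A reader might infer that Visit 2-3 infections go unobserved. Weekly surveys run to Visit 4 (Protocol 5.5.2.2). The gap is that these infections are not excluded.

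**Moving the window would create a new fault.** One might replace Visits 1-2 with Visits 2-3 in group ii. That would keep people infected shortly before their COVID-19 dose, although Protocol 5.3.2 bars self-reported COVID-19 in the 3 months before enrolment. This stands, and the fix adds to the existing rule for that reason. No matching influenza criterion exists for group iii, but an infection just before the dose would disturb its pre-dose titre too.

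**Conclusion.** The concern holds for exploratory results only. SAP 6.3 and 6.4 apply one calendar interval to every arm, and nothing excludes infection between Visits 2 and 3 for group ii's COVID-19 response or group iii's influenza response. Under the literal i v ii reading of SAP 9.2 the fault reaches a formal SARS-CoV-2 comparison. Under i v iii it is confined to descriptive results and to any general concomitant v sequential comparison made under the protocol.

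The likely direction is against concomitant dosing. The 1.4-15% range depends wholly on the assumed infection share and fold boost; its top needs 10% infected with a 4-fold boost. It shows scale and does not estimate the bias. The documents set no margin against which to judge it. The change is worth making because it is cheap and touches the study's central question for the second vaccine.

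**What to change.** 1. In SAP 9.2, name the arms for the SARS-CoV-2 contrast.
2. Wherever group ii's COVID-19 response or group iii's influenza response is analysed, keep the Visit 1-2 exclusion and add exclusion of infection between Visits 2 and 3.
3. In SAP 6.3 and 6.4, state that the required samples are the pre-dose and first post-dose draws for the respective vaccine, in line with Appendix 1 item 3.
4. Report infections by arm for each interval (Visits 1-2 and Visits 2-3).

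**Cost.** SAP wording only. Weekly surveys continue to Visit 4, and Protocol 5.7.2 collects documented infections to the end of the study, so no new data are needed. A few more later-dosed participants leave the exploratory analyses. Those who remain must be infection-free over two intervals, where arms dosed at Visit 1 need only one. Item 4 lets a reader see how much that matters.

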# 7 GENERAL ISSUES FOR STATISTICAL ANALYSIS

Data analysis will be performed using SAS version 9.4 software (SAS Institute Inc., Cary, NC) or R software (R Core Team, Vienna, Austria).

## 7.1 Multicenter Studies

There are 7 sites participating in the study. Data will be pooled across investigational sites for analysis purposes. A fixed site effect will be included in all analyses of the primary objective.

## 7.2 Handling of Dropouts, Missing Data

Missing immunogenicity values are considered missing completely at random (MCAR) and imputation methods will not be used.

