8 STATISTICAL ANALYSIS

8.1 Study Populations

There will be two study populations: the modified Intent-to-Treat (mITT) and Immunogenicity populations. The mITT population will include any participant who was enrolled, randomized, and received at least one vaccine. The Immunogenicity Population is a subset of the mITT Population that includes only subjects who received at least one vaccine, provide visit 1 and visit 2 blood draws available for analysis within the protocol-defined time frame, and with no protocol violations affecting immunogenicity. These protocol violations will be listed in the Statistical Analysis Plan. Statistical analyses of safety outcomes will be performed for the mITT population, and immunogenic outcomes will be analyzed for the Immunogenicity Population.

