# 6 ANALYSIS POPULATIONS

## 6.1 Intent-to-Treat (ITT)

The ITT population will include any participant who was enrolled and randomized.

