## 6.2 Modified Intent-to-Treat (mITT)

The mITT population will include any participant who was enrolled, randomized, and received both vaccines.

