### 8.2 Demographics

Demographic information including age, sex, race, ethnicity, and enrollment site will be presented by treatment group. Summary statistics (e.g., mean, standard deviation, median) will be presented for continuous variables. Categorical variables will be described with frequencies and percentages.

Demographics for the ITT population will be presented.

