### *Safety*

Safety endpoints will be assessed using the mITT population.

Frequency and proportion of participants reporting injection site and/or systemic reactions during the first 3 days following each vaccination visit will be stratified by severity and their impact on health, and reported along with the difference in proportions reporting moderate/severe symptoms between groups and a 95% confidence interval for the difference.

Frequency and proportion of participants reporting a change in health status requiring hospital admission (including a description of the event) during the study period will be reported along with the difference in proportions between groups and a 95% confidence interval for the difference.

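### The primary comparison of group i with group ii has no supportive analysis by assigned arm, although exclusion routes differ between the arms and missing titres are assumed MCAR

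*SAP*

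**What the plan says.** SAP 9.1 opens with "The primary objective will be analyzed using the immunogenicity population" and adds "All endpoints will be assessed with two-sided tests and alpha set to 0.05". The contrast is group i (both vaccines at day 0) against group ii (influenza vaccine at day 0, COVID-19 vaccine at day 28). SAP 6.3 defines the Influenza Immunogenicity Population, which I take to be the set meant. A participant must have received both vaccines, have in-window HAI results at Visits 1 and 2, have had no influenza or SARS-CoV-2 infection between those visits, and have none of the violations in SAP Appendix 1. Items 6 and 7 of that list are delayed and missed vaccine administration.

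On missing data, SAP 7.2 says "Missing immunogenicity values are considered missing completely at random (MCAR) and imputation methods will not be used".

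The wider sets have little or no role in the immunogenicity results. SAP 6.1: "The ITT population will include any participant who was enrolled and randomized". Its one stated use is in SAP 8.2: "Demographics for the ITT population will be presented". The SAP's mITT set serves safety ("Safety endpoints will be assessed using the mITT population"). SAP 6.2 defines it as "The mITT population will include any participant who was enrolled, randomized, and received both vaccines", whereas Protocol 8.1 has "The mITT population will include any participant who was enrolled, randomized, and received at least one vaccine".

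Two provisions bear on the point. SAP 6.3 plans an additional analysis that restores participants who missed the visit window, if they number at least 10% of the total study population. SAP 8.1 plans a flow chart by age and randomisation group, counts of completed and missed visits, and a breakdown of the analysis populations.

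**The concern.** Randomisation protects the comparison of the arms as assigned. The primary analysis instead compares those who remain after events that follow randomisation. If the arms lose different kinds of people, the difference in who is left is read as an effect of the schedule. It could create a difference or hide one.

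The plan has no second analysis from which a reader could see whether the result depends on the exclusions. It also declares, rather than examines, that missing titres are unrelated to anything. The models in SAP 9.1 account for site only. The Visit 1 titre, an obvious predictor of the Visit 2 titre and available for most participants, is not named as a covariate.

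**Working it through.** **Step 1. Compare the routes out of the analysis set.**

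| Route | Group i | Group ii |
|---|---|---|
| Second dose missed (SAP 6.2, 6.3; Appendix 1 item 7) | No Visit 2 dose to miss | Excluded, even with valid Visit 1 and Visit 2 HAI results |
| Second dose delayed (Appendix 1 item 6; delay criteria in Protocol 5.3.3) | No Visit 2 dose to delay | Excluded |
| Infection between Visits 1 and 2 (SAP 6.3) | Has had the study COVID-19 vaccine | Has not yet had it |
| Missed or late Visit 2 blood | Possible | Possible |

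Protocol 5.1 schedules the Visit 2 blood draw before the Visit 2 vaccination. For group ii, the first two rows therefore discard a primary outcome because of something that happens after it was measured.

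**Step 2. Test the reach of the additional analysis.** The trigger counts window-missers in the whole trial: 10% of 800 = 80. So 79 could be lost without setting it off. Group ii has 150 + 50 = 200 participants, so at the extreme 79/200 = 39.5% of that arm. When triggered, it relaxes the window rule only. Both vaccines, no infection and no other violation are still required.

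**Step 3. Illustrate the size.** Neither document states power, SD, effect size or dropout rate, so there is no planned figure to reproduce. The inputs from the documents are the allocation (300 + 100 = 400 in group i, 150 + 50 = 200 in group ii, ages pooled) and alpha of 0.05, two-sided. The exclusion shares and the selection are assumptions.

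Let m be the share excluded in an arm, and d the mean of those kept minus the mean of those excluded, in SD units. The mean of those kept exceeds the full-arm mean by m × d. With no true difference:

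- bias = m₁d₁ − m₂d₂
- SE = √(1/n₁ + 1/n₂), with n the numbers kept
- type I error = Φ(−1.96 + |bias|/SE) + Φ(−1.96 − |bias|/SE)

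With 5% v 10% excluded and d = 0.5 in both arms: bias = 0.025 − 0.050 = −0.025. The numbers kept are 380 and 180, so SE = 0.0905 and |bias|/SE = 0.276. Type I error = 0.046 + 0.013 = 0.059.

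With 5% v 15%: bias = 0.025 − 0.075 = −0.05. The numbers kept are 380 and 170, so SE = 0.0923 and the ratio is 0.542. Type I error = 0.078 + 0.006 = 0.084.

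| Excluded, i v ii | d | Absolute bias (SD) | Type I error |
|---|---|---|---|
| 10% v 10% | 0.5, both arms | 0 | 0.050 |
| 5% v 10% | 0.25, both arms | 0.0125 | 0.052 |
| 5% v 10% | 0.5, both arms | 0.025 | 0.059 |
| 5% v 15% | 0.5, both arms | 0.05 | 0.084 |
| 5% v 15% | 1.0, both arms | 0.10 | 0.192 |
| 10% v 10% | 0.5, opposite directions | 0.10 | 0.195 |

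If the SD of log2 titre were 1.6 (assumed), biases of 0.025 and 0.05 SD would be 0.04 and 0.08 log2. These are GMT ratios of 2^−0.04 = 0.97 and 2^−0.08 = 0.95 when the truth is 1. The last row shows that equal counts in the flow chart would not by themselves rule out bias.

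**The case against.** The immunogenicity population is a deliberate choice. Protocol 8.1 assigns immunogenicity outcomes to such a population, and the primary objective asks about titres after the vaccines as given. The reasons for exclusion are fixed in advance, and SAP 8.1 would make unequal loss at least partly visible. All of this stands. It supports keeping the population as the primary set, but does not remove the need for a supportive analysis.

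A reader might infer three stronger things that the documents do not support.

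- *That MCAR is the plan's only justification for its exclusions.* SAP 7.2 concerns missing values. Participants with titres are excluded under SAP 6.3 and Appendix 1, which do not depend on it.
- *That group i, returning only for blood, must bias the result.* Unequal return alone does not bias the means; return must also be related to titre. Both arms must attend Visit 2, and participants are not told their titres (Protocol 5.2.1.1).
- *That a GMT ratio near 0.88 is to be expected when the truth is 1.* Such a figure can be simulated with 20% v 10% loss, giving a bias of −0.189 log2. With equal SDs at the two visits and a pre/post correlation of 0.6, it needs a Visit 1 shift of 0.189/0.6 = 0.315 log2. That means attenders and non-attenders differing by 0.315/(0.20 + 0.10) = 1.05 log2 in opposite directions by arm, or by 0.315/0.20 ≈ 1.6 log2 in group i alone. Nothing in the documents suggests selection that strong. For fold rise the slope on the Visit 1 titre would be 0.6 − 1 = −0.4, so the same scenario gives a smaller bias of opposite sign.

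The direction is also open. The second-dose and infection rules would tend to remove more of group ii, whereas a weaker reason to return would remove more of group i. The two could offset.

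**Conclusion.** The gap is real and cheap to close. The primary comparison rests on one post-randomisation, complete-case set whose exclusion rules do not act alike on the two arms, and no analysis by assigned arm stands beside it. The clearest defect is the loss of group ii participants whose valid Visit 2 sample precedes the dose they miss or delay.

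The documents do not establish that bias will occur, how large it would be, or which arm it would favour. It is zero under MCAR. With 5% v 10% to 5% v 15% excluded and 0.5 SD selection, it is 0.025 to 0.05 SD, with type I error of about 0.06 to 0.08 against a nominal 0.05. These figures rest on assumed exclusion and selection, and on 400 v 200 with ages pooled. Protocol 4.1 and SAP 3.1 mention HAI in a subset of samples, so the tested numbers may be smaller. The point is a recommended improvement and does not invalidate the primary analysis.

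**What to change.** Keep the Influenza Immunogenicity Population as the primary set, and make these changes.

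- **SAP 9.1, endpoints i to iv:** add a supportive analysis by randomised arm of all randomised participants with Visit 1 and Visit 2 HAI results, regardless of second-dose receipt, infection or Appendix 1 violations.
- **SAP 7.2:** replace MCAR with MAR given arm, site, age group and Visit 1 titre. For GMT and GMFR, fit a constrained longitudinal model of log2 titre at Visits 1 and 2 (a common baseline mean across arms) to everyone with at least one titre.
- **SAP 8.1:** report exclusions by arm and reason.
- **SAP 6.3:** state that individual exclusion decisions are settled before HAI results are linked to arm.
- **SAP 6.2 and Protocol 8.1:** reconcile the two mITT definitions.

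The first analysis undoes the exclusions but is still complete-case. Only the longitudinal model deals with missing titres, and it covers GMT and GMFR, not the two binary endpoints. The cost is a few extra model runs and one more table, with no new data.
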